## **8. Study Procedures**

**a. Study Design**

Aim 1 (A1): Co-create plans for optimizing Measurement Based Care (MBC) implementation for youth with comorbidities.

***Site visit 1 (2 days)***

**A1a MBC Training.** We will kick off the site visit with a 2-hour orientation/training about Measurement Based Care for which therapists can receive CEUs. At the end of the training, we will ask them to complete IMPACT's center-wide 18-item Implementation Climate Scale over REDCap (ImplementationClimateScale\_NIMBLE REDCap.pdf submitted in this package.

**A1b. Rapid Ethnographic Assessment (REA).** REA plan was developed in conjunction with two REA experts (Gray and [name]). REA will be conducted over 2-day site visits (in-person or virtual) at each clinic, following the kickoff training, by **[name]** (project co-lead), **[name]** (project manager), and research specialist (**[name]**). For in-person visits, this team will conduct ethnographic observations on both days, using primarily unobtrusive techniques on Day 1, documenting observations of activities (e.g., clinician documentation), interactions (e.g., client check in), and events (e.g., staff meeting) using written and audio-recorded field notes. The team will try to engage all clinic staff in ethnographic interviews with questions in 4 categories. Grand tour: Could you describe a typical day at this clinic? Mini tour: Could you describe a typical therapy session? Task: Could you show me how you use MBC in your work and describe what you are doing? Example: Could you give me examples of "good" and "poor" use of elements of MBC? No identifying information will be collected, and all staff/therapists will be identified by a STUDY ID.

We will interview staff for responses to the "example" question described above. We expect up to 30 interviews per clinic: 30–45 minutes for therapists, 15 minutes for staff. We will synthesize learnings from observations, interviews, and surveys in a debriefing session, using notes to generate a list of unique barriers.

Day 2 (if in person) will be focused observations of therapists shadowed by team members to document, track, and note the duration and location of activities, guided by barriers identified

in the evidence review and Day 1 learnings. We will conduct semi-structured, focused interviews virtually or in-person based on Day 1 learnings, with therapists (therapists, supervisors, psychiatrists) and staff (up to 30). Day 2 interviews will be longer (15-30 minutes) and audio recorded if done in person.

If study activities are done virtually, there will be no site observation, but the study team will conduct interviews. In this case, videos will be video recorded and transcribed using the Microsoft Teams platform.

**A1c. Design Kits.** To complement REA and collect real-time data from therapists and youth, at the end of site visits, we will leave (or mail) design kit materials including disposable cameras, journals, pens and prompts to use to describe using MBC by taking pictures, make diary entries, draw maps, and record images. We will ask therapists (5-8 per clinic) to participate. We will strive to recruit at least one youth from each participating therapist to also complete design kits.

We will recruit 5-8 youth clients to also complete design kits. This is the only youth-related activity in the study. Participants (*therapists and youth*) will have one week to document experiences before returning the toolkits to the study team in self-addressed, postage-paid stamped envelopes. Within a week of receiving the data, team members will conduct follow-up 15-minute phone interviews, inviting participants to interpret and comment on their responses. Team members will create memos documenting barriers and describing their salience, meaning, and importance to the participant.

#### **A1d. Barrier Prioritization.**

We will engage 5-8 therapists and/or staff in the prioritization activity for a 2-hour facilitated group activity. The activity will occur in-person (Site Visit 2) but could be delivered virtually if needed. Barriers identified through the rapid evidence review, rapid ethnographic assessment, and design kits (50+ expected) will be prioritized using a participant-engaged method. We will begin by showing clinic staff/therapist participants a list of identified barriers grouped by level (e.g., individual therapist, clinic-level, supervisor-level) and ask them to rank their 20 most important barriers. After, we will ask them to rate how important, long-lasting, and pervasive those barriers are in their use of MBC. These meetings will not be recorded.

**A1e. Causal Pathway Diagramming.** For each clinic, we will develop **Causal Pathway Diagrams** CPDs for the top 3 prioritized barriers. The goal is to assess how well each implementation strategy is matched to a prioritized barrier, based on its mechanism of action, and to clarify the causal chain of events that must take place to achieve MBC fidelity. Our research team will develop a CPD for the top barrier, to use as an example, in advance of meeting with the same group of 5-8 therapists and staff in each clinic who participated in the barrier prioritization activity (Site Visit 2). We will present the CPD, introduce clinic staff participants to the 5-step construction process, discuss how the CPD aligns with their experiences, and modify it as needed. We will then collaboratively guide

clinic staff participants in constructing CPDs for the other barriers using the 5-step process described below. Plain language questions will be used to guide stakeholders through the process of developing CPDs. These meetings will be recorded using the Microsoft Teams platform if done virtually.

**A1f. Focus Groups to Improve IMPACT methods.** We will engage our partners in a semi-structured focus group to capture their experience engaging in all IMPACT Center methods in the 3 site visits to inform further toolkit refinement. A facilitator not previously engaged in any of the activities will conduct a 90-minute focus group to solicit reactions to all aspects of IMPACT's methods, including the steps and personnel requirements of each method, and their output (e.g., prioritized barriers; utility of the information captured in the CPDs). We will also be collecting implementation outcome measures, Acceptability, appropriateness, feasibility using established measures. The focus group data will supplement observer notes taken throughout the site visits.

To gather quantitative data related to IMPACT methods, up to N = 30 workshop participants will also be asked to complete Weiner et al.'s (2017) acceptability of intervention measure (AIM), feasibility of intervention measure; (FIM), and intervention appropriateness measure (IAM). The focus of these measures will be on assessing the acceptability, feasibility, and appropriateness of IMPACT center methods (e.g., design kits). These measures are uploaded in the IRBNet submission.

**AIM 2 (A2): Compare MBC fidelity post IMPACT Center methods deployment versus historical controls.** To examine MBC fidelity in Aim 2, we use routine session process data entered by therapists as part of their participation in the Washington CBT+ Initiative. In addition, we will request that therapists fill out a short anonymous self-reported survey on outcome use before the active implementation period, at 3 months and again at 6 months (REDCap survey: MBC Outcome Questionnaire).

[name] is a co-director of the Washington State CBT+ Initiative and the MPI of the IMPACT center. The dashboard with de-identified cases from which we are collecting data from is maintained as part of the CBT+ Initiative, and the CBT+ Initiative is the primary "laboratory" for IMPACT center methods. When data from CBT+ aligns with IMPACT aims, data can be curated by their team and sent to IMPACT NIMBLE co-investigator [name], via secure file transfer per CBT+ operational guidelines and procedures. Data will be shared back with clinics and the CBT+ initiative only in aggregate form for the purposes of quality/continuous improvement. CBT+ has routinely used data from the dashboard for quality improvement over the past 10 years.

Historical data has already been collected and is available to the study team as part of their involvement in the CBT+ initiative and ongoing practice improvement work. As part of

their clinic training, each therapist in these clinics participates in a CBT+ training. For the training, they track MBC data for up to 5 cases. To log the data for these 5 cases, therapists log into an account set up for them by an administrator and enter the data under a pseudonym. They can choose any code (e.g., “Marty McFly”) to identify their patient so long as it does not contain the name of their patient or any other identifying information. Thus, all client-level data are de-identified before they are entered into the system. While administrators have access to website data that contains therapist names and other information, that information is not and will not be accessible to this study team.

For post-IMPACT comparison data, therapists providing data will fall into two categories. The first category are therapists who have not gone through the CBT+ training yet. These therapists will follow the same procedures as those who entered historical data. The second category are therapists who have already completed their CBT+ training. We will ask the second category therapists to track data for 5-8 new cases. They will go through the same procedure as the other therapists with one exception. Rather than creating codes to identify patients themselves, our study team will have each therapist select a paper list of up to 8 identifying codes (e.g., AA1, AA2...AA8) to use to identify their patients. We will not keep any document that links any specific codes to any therapist. In this way, we will be able to isolate data identified by those codes, and identify that they came from a therapist within a specific clinic, but we will not be able to identify therapists individually.

**Data Collection Instruments** (these documents have all been uploaded to IRBNet:

Clinic Site Visit interviews: Supervisor-level interview guide, Management-level interview guide, Clinician-level interview guide, Admin Support Interview guide, AIM FIM IAM measures, and Implementation Climate Scale.

NIMBLE Youth Design Kits: Youth Design Kit Instructions, Youth Activity Cards, Follow-up design kit interview.

NIMBLE Clinician Design Kit: Clinician Design Kit Instructions, Clinician Activity Cards, Follow-up design kit interview.

Implementation outcome scale (AIM FIM IAM measures.docx) – Package 1

Implementation Climate Scale: ImplementationClimateScale\_NIMBLE REDCap.pdf – Package 1  
and electronic/REDCap version in current package

MBC Fidelity Outcome self-report scale: MBCOutcomeQuestionnaire\_NIMBLE(2).pdf – Package 6

 **Table 2. Overarching Timeline and Activities**

	Activities	Months 0-6	Months 6-12	Months 12-18	Months 18-24	Months 24-30	Months 30-36
A1	Clinic Enrollment & Engagement	x					
	Participant Enrollment		Chrt 1	Chrt 2	Chrt 3		
	Manuscript Preparation				x	x	x
A2	Evidence Review	x					
	Site Visits 1-3		Chrt 1	Chrt 2	Chrt 3		
	Debrief Focus Group		Chrt 1	Chrt 2	Chrt 3		
A3	Toolkit Data Extraction			Chrt 1	Chrt 2	Chrt 3	
	Historical Control Data Analysis			Chrt 1	Chrt 2	Chrt 3	

**b. Data Analysis**

**Aim 1** – The purpose of all data collected in aim 1 is to identify barriers to the use of measurement-based care. All rapid ethnography and design kit data will be used to this end.

**Rapid Ethnography data analysis will occur in four main steps.**

**Step 1: Data Condensing.** All data sources will be compiled as text and entered a Microsoft Excel database. We do not anticipate any names will appear in these data, but if names do appear they will be deleted. Data triangulation will consist of word clouds and heat maps.

**Step 2: Data Reduction.** At least two team members will read all text data gathered in the project. Two team members will iteratively code data into themes.

**Step 3: Data Interpretation.** We will categorize coded data with the explicit purpose of (1) identifying barriers (what is getting in the way of MBC use), (2) identifying facilitators (are there established strengths we can leverage to strengthen MBC use), and (3) identifying themes that may aid in development of implementation strategies (do clinic staff participants identify possible solutions for overcoming barriers).

**Step 4: Data Representation.** Ultimately, these data will be used to generate a list of clinic-specific barriers categorized as in Lewis et al., 2019. Barriers identified through this process may be represented in several ways (e.g., box display, matrix, network) depending on the content and form of codes and categories.

**Design Kit data analysis will occur in five main steps, with only Step 1 differing from REA.**

**Step 1: Data description and transcription.** Visual data (photos) will be described by two members of the study team. While we do not anticipate any identifying information in photographs, we will first inspect and shred any photograph that includes any possible identifying information. Second, two members of the study team will jointly create visual descriptions of photos. Journal information will be transcribed into a Microsoft form. All names or other identifying information will be removed.

**Steps 2-5:** The study team will undergo the same steps as rapid ethnography to identify a list of barriers: data condensing, data reduction, data interpretation, and data representation.

**Aim 2 – Analytic Plan**

Analyses will be the same for each fidelity outcome tool. We will use 3-level generalized mixed effects models to account for the multilevel nature of the data (fidelity score nested within therapist nested within clinic). Significance of model fit and individual coefficients will be

determined via deviation tests (likelihood ratio, Akaike Information Criterion, & Bayes Information Criterion).

**Power.** Assuming parameters outlined above, therapist intraclass correlations ranging from .01 to .30, and level-2 covariates correlating with outcomes at .15, we have power of .80 to detect a minimum effect size of  $d = .36 - .48$

Data from each clinic will be collected and combined into a primary dataset after the 12th month of their involvement, or when enough therapists have completed entering their 5 training cases into the CBT+ dashboard. Data cleaning and primary analyses will begin once all data from all participating clinics are collected and compiled into one dataset. It is expected that analyses will take between 3 - 6 months after data are gathered from the final clinic to complete. The primary outcomes paper will be written between 4 months - 1 year after data are analyzed.

#### **c. Sharing of Results with Participants**

Throughout the study, Study Team Members will work with participating clinic staff, sharing feedback as aggregate data reflecting what we have learned and ask for clinic staff to reflect on how current clinic state matches data interpretation by study staff. This is important for surfacing any factors that need to be addressed during the implementation process to optimize MBC.

There are no study results to provide to individual participants. Youth will not receive any results.

#### **d. Data and/or Specimen Banking**

N/A

### **9. Privacy, Confidentiality and Data Security**

#### **a. Privacy during Study Activities**

The data collected for this study: REA interviews, Youth and Therapist Design Kits, Barrier Prioritization, Causal Pathway Diagramming, and Focus Groups, does not contain personal information, it is information related to how the participant experiences or implements Measurement Based Care at the CMHC participating in this study. However, we will protect confidentiality by using Study ID instead of names. Electronic files collected by design kit study participants (if they choose to use this format instead of or in addition to our disposable cameras) will be transferred to the research team at KPHRI via SFT. All files will be stored on the KPHRI G-drive or Sharepoint site with access only granted to research staff granting access. All computers at KPHRI are password protected and employees are trained in data safety and sign confidentiality agreements annually.

#### **b. Storage of data and/or specimens.**

All data will be stored on password-protected computers on the study G-drive accessible only to IMPACT Center Study Staff or on the KPWA REDCap platform. Physical documents will be stored at MPE in locked filing cabinets only accessible to study staff. All materials will be de-identified, using a unique study ID that does not require a crosswalk because we only need to know which

documents correspond with each other. Because this is de-identified data, it will be kept indefinitely. Postage paid self-addressed sealed envelopes will be sent back by USPS. All audio and digital recordings of rapid ethnography interviews will be kept on the G-drive or Sharepoint site with access only granted to research staff on the IRB.

**c. Collection of data from participants electronically**

If Clinic staff participants prefer, we will communicate via email to convey basic study information such

as to confirm interview times and send information for how to join meetings via Zoom/Teams or to answer questions about completing Design Kit Activities. No PHI is being collected as a part of this study.

In addition, we will set up a secure file transfer so that the participants can upload any potential electronic data collected while completing Design Kit activities to the study team. Participants are instructed not to collect any personally identifying information in their electronic data, so this data will

not contain personal information or PHI. The Implementation Climate Scale (ImplementationClimateScale\_NIMBLE REDCap.pdf) and NIMBLE Outcome Questionnaire (MBCOutcomeQuestionnaire\_NIMBLE(2).pdf) do not collect any PHI and will be distributed via the REDCap survey distribution tool, which is secure.

Youth will not be contacted by Zoom/Teams; youth will only be contacted by telephone.

**d. Disclosure of PHI to Collaborators**

We are not collecting PHI from collaborators. We will give participating therapists a list of 8 pseudonyms to enter youth data under in the Washington State CBT+ Initiative dashboard. When we access the data, we will be able to limit what we gather to the pseudonyms provided. This will allow for us to not link youth to therapists.

**e. Funder required data sharing**

The IMPACT Center, funded by NIMH will share 2 measures which are being collected across all studies:

1. Implementation Outcomes Measure
  - a. Appropriateness
  - b. Feasibility
  - c. Acceptability
2. Causal Pathway Diagrams

**None of the measures listed above contain PHI, patient data, clinical data, individual data, or any identifiable data.**

**f. Data and specimen sharing (data commitments)**

N/A

[name] will access any sensitive study information and perform study activities through a KP laptop, provided to him after he became an "unpaid member of the workforce." He will access data through the GlobalProtect VPN. No DTAs are needed at this time.

**g. Data provided from external organizations or other KP regions**

N/A

**10. Provisions to Monitor Data to Ensure the Safety of Participants**

N/A

**11. Risks and Benefits**

**a. Risks to Participants**

While we will hold conversations about workflow at the clinics, we will not be discussing individual level performance, nor reporting any individual outcomes. There is minimal risk that an employee would suffer any adverse outcome based on the data we are collecting and sharing.

The only risk for clinic staff/therapists is the possibility that their Design Kit could be intercepted by someone not involved in the project, however, this risk is minimized because we are not collecting any PHI or personal information in the Design Kit process.

One possible risk for youth is that their parent finds their design kit journal, however, there is no detailed information about their mental health or treatment plan, it would likely look like a school project. The youth could feel uncomfortable or upset that their parent had read their journal. The only possible risk with youth is that their de-identified design kit will be intercepted in the mail, which is highly unlikely given that they will be provided with a pre-paid, sealable envelope. While we do have to mail the Design Kits to the youth, the materials in the Design Kit are identified by Study ID only and the return envelope does not include participant name or address.

**b. Potential Benefits to Participants**

There is no direct benefit to participants in this study. They may have indirect benefits of feeling like they have contributed to science.

**12. Costs to Participants**

Participants will not be responsible for any costs.

**13. Compensation to Participants**

For the design probe/kit activity participants will be compensated for their time and effort; therapists will receive a \$100 gift certificate and youth will receive a \$50 gift certificate.

Therapists who participate in the MBC workshops will receive continuing education units (CEU). Clinic staff and therapists will receive \$25 gift certificate for participating in clinic visit interviews. Clinic staff and therapists will receive a \$100 gift certificate for participating in focus groups.

#### **14. Drugs or Devices**

- a. Drug Study:** N/A
- b. Device Study:** N/A

#### **15. Qualifications and Human Subjects Training Assurance**

PI attestation: Study investigators are responsible for assuring that all study team members have required HIPAA and human subjects training. KP key personnel are required to link CITI training records to their IRBNet profile. Check the following to confirm:

- All study staff (at KP or at other sites if relying on the KPiIRB for IRB review) who have access to identifiable data, or who interact with participants (e.g., programmers, research specialists, survey interviewers, interventionists, etc.) have up-to-date HIPAA and human subjects training records. KP training requirements are established by the regional research centers or research compliance functions.
- All study activities will be conducted by individuals with appropriate training, education, including licensure and language competency. If this cannot be confirmed, explain:

#### **16. Additional Approvals/Ancillary Reviews**

N/A

Statistical Analysis Plan

Title: Novel Methods for Implementing Measurement-Based Care for Youth in Low-resource Environments

NCT number: NCT05644756

Date of this analytic plan: 5/5/2025

Statistical Analysis Plan

Original analytic plan: Analyses will be the same for each fidelity outcome tool. We will use 3-level generalized mixed effects models to account for the multilevel nature of the data (fidelity score nested within therapist nested within clinic). Significance of model fit and individual coefficients will be determined via deviation tests (likelihood ratio, Akaike Information Criterion, & Bayes Information Criterion).

Power. Assuming parameters outlined above, therapist intraclass correlations ranging from .01 to .30, and level-2 covariates correlating with outcomes at .15, we have power of .80 to detect a minimum effect size of $d = .36 - .48$

Data from each clinic will be collected and combined into a primary dataset after the 12th month of their involvement, or when enough therapists have completed entering their 5 training cases into the CBT+ dashboard. Data cleaning and primary analyses will begin once all data from all participating clinics are collected and compiled into one dataset. It is expected that analyses will take between 3 - 6 months after data are gathered from the final clinic to complete. The primary outcomes paper will be written between 4 months - 1 year after data are analyzed.

UPDATES: We deviated from the original analytic plan because we were unable to recruit clinicians to track outcome data using the CBT+ toolkit. Instead, and as documented in the protocol, we sent providers a Qualtrics form asking them to self-report their caseload as well as the number of clients they reported using measurement-based care with. The updated analytic plan based upon this change is as follows: Descriptive statistics will be used to summarize fidelity to measurement-based care (MBC) at each of the three assessment time points. A repeated-measures analysis of variance (ANOVA) will be conducted to evaluate whether fidelity to key components of MBC changes over time—from baseline (defined as 6 months post-enrollment) to 3 months after the conclusion of active implementation, and again at 6 months post-implementation. No statistical corrections for multiple comparisons will be applied given the single statistical test being carried out. Statistical significance will be evaluated at the 0.05 level (two-tailed). To address missing data, a conservative **Last Observation Carried Forward (LOCF)** approach will be used, allowing participants with partial data to be retained in the analytic sample. Assumptions of normality and sphericity will be assessed. If the assumption of sphericity is violated, Greenhouse-Geisser corrections will be applied. Effect sizes (e.g., partial eta squared) will be reported to estimate the magnitude of observed effects. All analyses will be conducted using R v4.3.3 and Rstudio 2023.12.1].

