### **c. Secondary Objectives/Aims**

#### **AIM 2: Compare MBC fidelity post IMPACT Center methods deployment versus historical controls.**

We will evaluate at the clinic level whether IMPACT methods were effective in optimizing MBC fidelity. To do this, we will employ two methods: 1) an **anonymous self-report survey** pre-implementation, 3 months and again 6 months post implementation strategies, and 2) a historical control design comparing MBC fidelity pre- and post- IMPACT methods (e.g., design kits). **Pre-IMPACT method** data will be captured from a pre-existing, routinely gathered, de-identified database from the Washington State CBT+ initiative (**further described in Section 6 – Setting**). The database will represent MBC fidelity 2 years prior to IMPACT center methods. For **post-IMPACT method** data, at least 5 therapists at each clinic will be asked to report MBC fidelity data to the Washington State CBT+ Initiative Dashboard for up to 5 cases. Therapists at each clinic are familiar with the Dashboard, as its use is part of their routine training. Data recorded related to MBC fidelity consists of therapist's use of the three main components of MBC – (1) Collect, (2) Share, and (3) Act (described further in **Scientific Background** and **Study Procedure** sections).

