**This study is the first signature project of the IMPACT center in partnership with the Washington State CBT+ initiative.** The current project uses new methods, including rapid evidence synthesis, rapid ethnography, and design kits to identify locally contextualized barriers to clinic-wide use of MBC, as well as causal pathway diagramming (CPD) a method for selecting strategies and matching them to barriers that will help clinics optimize their use of MBC (Aim 1.) We will investigate whether IMPACT methods improve MBC fidelity through a historical control design (Aim 2).

[figure not shown]

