**Aim 2 (A2): Compare MBC fidelity post IMPACT Center methods deployment versus historical controls (no site visit)**

The purpose of IMPACT methods is to improve clinician's fidelity using MBC. Fidelity will be conceptualized as therapist's use of the three main components of MBC – (1) Collect, (2) Share, and (3) Act. We will assess fidelity in two ways. First, we will use a brief anonymous self-report survey before implementing strategies and 6 months after. Previously, we had planned to use data from the Washington State CBT+ Initiative Dashboard, but we have had difficulty recruiting clinicians to engage in this task. For our second method of fidelity measurement we will ask clinics to send a dataset from their electronic health record for at least 6 months before IMPACT methods were deployed, and to 6-months after the active implementation period. The dataset will not contain any PHI. We will compare historical data at 6- and -18 months post site visits. .

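### The SAP's single planned test, an omnibus F for any change over three time points, has no direction, while Aim 2 asks whether MBC fidelity improved.

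*SAP*

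**What the plan says.** The SAP keeps the three-level mixed model only as the original plan and says it was departed from. Under UPDATES it promises descriptive statistics at baseline and at 3 and 6 months after active implementation, followed by one inferential analysis: "A repeated-measures analysis of variance (ANOVA) will be conducted to evaluate whether fidelity to key components of MBC changes over time". Significance is judged two-tailed at 0.05, with a Greenhouse-Geisser correction if sphericity fails. On the number of tests it says: "No statistical corrections for multiple comparisons will be applied given the single statistical test being carried out". On effect size it says: "Effect sizes (e.g., partial eta squared) will be reported to estimate the magnitude of observed effects". It names no contrast, pairwise comparison, trend test or primary time point, and no confidence interval.

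The protocol states the Aim 2 question three times, each time with a direction:

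- Section 2c: "We will evaluate at the clinic level whether IMPACT methods were effective in optimizing MBC fidelity".
- Section 3a: "We will investigate whether IMPACT methods improve MBC fidelity through a historical control design (Aim 2").
- Section 4, Aim 2: "The purpose of IMPACT methods is to improve" clinicians' fidelity in using MBC.

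**The concern.** With three time points, the repeated-measures F has two numerator degrees of freedom. It asks whether the three means are equal. It does not ask whether a later mean is higher than baseline. Partial eta squared is a share of variance and has no sign. The two-tailed setting does not give such an F a direction.

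The plan therefore tests whether anything changed, while the aim asks whether fidelity rose. A significant result could come from a lasting gain, from a gain at 3 months that is gone by 6 months, or from a fall. Only the first is a clear yes to Aim 2. If the choice between 3 and 6 months is left until the means have been seen, any claim of improvement rests on a comparison that was not planned.

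**Working it through.** **The plan's own figure.** The SAP gives a minimum detectable effect of d = .36 to .48 at power .80. It belongs to the superseded mixed model, and its design inputs (therapists and cases per period) are not stated, so it cannot be reproduced. A two-period formula with 30 against 30 therapists and 5 cases each comes closest, at .33 to .48. No power figure is given for the ANOVA. The check below borrows .36 and .48 only as illustrative shifts.

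**Inputs.** From the documents: three time points, alpha 0.05, and n = 30 (the protocol's Aim 2 number, which is not tied to the revised survey). Assumed: normal scores with SD 1, compound symmetry, within-therapist correlation rho of 0.2 to 0.8, responses linked within therapist, no clinic clustering and no missing data.

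**Step 1: three patterns, one noncentrality.** Order the means as baseline, 3 months, 6 months.

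- Sustained gain (0, d, d): the mean is 2d/3, so the squared deviations sum to 4d²/9 + d²/9 + d²/9 = (2/3)d².
- Gain lost by 6 months (0, d, 0): the mean is d/3, so the sum is d²/9 + 4d²/9 + d²/9 = (2/3)d².
- Sustained fall (0, −d, −d): as for the first pattern, (2/3)d².

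The noncentrality is lambda = n(2/3)d²/(1 − rho) for all three. The power of the F is therefore identical for the three patterns, whatever n, d and rho are.

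**Step 2: power of the F, with 2 and 58 degrees of freedom.** For d = .48, 30 × (2/3) × 0.2304 = 4.608. Dividing by 0.8, 0.5 and 0.2 gives lambda = 5.76, 9.22 and 23.04.

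| d | rho | F, each of the three patterns | 6-month contrast, sustained gain |
|---|---|---|---|
| .48 | 0.2 | .54 | .52 |
| .48 | 0.5 | .76 | .72 |
| .48 | 0.8 | .99 | .98 |
| .36 | 0.2 | .33 | .33 |
| .36 | 0.5 | .50 | .48 |
| .36 | 0.8 | .89 | .85 |

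At d = .48 and rho 0.5 the expected partial eta squared is about (2 + 9.22)/(2 + 9.22 + 58) = 0.16, again the same for all three patterns.

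**Step 3: what a significant F says about 6 months.** In 100,000 simulated trials of the gain-then-loss pattern (n = 30, d = .48, rho 0.5), the F was significant in .76. In .38, half of those, the 6-month mean was below baseline.

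**Step 4: the signed contrast.** The 6-month-minus-baseline difference has variance 2(1 − rho), so its noncentrality is d√n/√(2(1 − rho)). At d = .48 and rho 0.5 this is 0.48 × 5.48/1 = 2.63 on 29 degrees of freedom, giving power .72 for a sustained gain (last column of the table). For a gain lost by 6 months the true difference is zero, and the contrast is significant in 5% of trials, 2.5% in each direction. For a sustained fall it is significant as often as for a gain, but with a negative sign. For a linear rise reaching .48 at 6 months its power is .72, against .63 for the F.

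**The case against.** The best defence is that the ANOVA will not be read alone. The SAP first commits to descriptive statistics at each time point, so a fall or a rise and return would be visible in the means. This stands, and it limits the harm: a reader might infer that a fall could pass unnoticed as a success, but the documents do not support that. What is missing is a test or an interval behind a statement that fidelity improved.

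Second, partial eta squared is given only as an example, so a signed effect size is not excluded. That is also right, but the SAP commits to none.

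Third, the ANOVA sentence runs from baseline to 3 months and then to 6 months, which might suggest two comparisons. None is specified, and the single-test statement rules them out.

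A reader might also infer that the multiplicity waiver is wrong, because the ANOVA sentence speaks of key components and protocol section 4 defines fidelity through "use of the three main components of MBC", which are Collect, Share and Act. The documents do not show this error. The form asked providers to "self-report their caseload as well as the number of clients they reported using measurement-based care with", which can yield one score, and the waiver is sound for one score. The questionnaire itself is not in the documents, so there is no basis for saying which score should be primary or for reducing the three components to description.

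Finally, Aim 2 is a secondary aim of a pilot. That bears on priority. It does not change whether the test matches the question.

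**Conclusion.** The point holds. The F is a valid test of any change, but it does not test the question that Aim 2 asks. The equality of power across the three patterns follows from the algebra, given compound symmetry, and needs no value of n, d or rho. The percentages are illustrative only: n, d and rho are assumptions, and clinic clustering and missing data are ignored.

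It would be too much to say that the ANOVA is invalid, or that a signed contrast is needed to gain power. The gain or loss depends on the pattern of change. For a sustained gain the 6-month contrast has slightly less power than the F, and for a linear rise it has more. The case for it is that it answers the stated question with a signed estimate. This should be changed, and confidence is high that the contrast is missing.

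**What to change.** In the UPDATES section of the SAP, keep the fidelity score that the SAP analyses and replace the single-test sentence with wording such as:

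> The one primary test is the 6-month-minus-baseline contrast of the fidelity score, two-sided at 0.05, reported as mean change with 95% CI. The 3-month-minus-baseline change, with 95% CI, is secondary. The omnibus time effect and partial eta squared are supportive.

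With one primary contrast, the single-test statement stays true for that score and no multiplicity correction is needed. The contrast should not wait for a significant F. At n = 30 and d = .48, requiring both would cut power for a sustained gain from .52, .72 and .98 to about .44, .66 and .98 at rho 0.2, 0.5 and 0.8. If the data have already been examined, label the contrast post hoc.

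One alternative is the average of the two follow-ups minus baseline. It has more power for a sustained gain (.84 at rho 0.5), but it is also significant in 31% of trials when the gain is gone by 6 months, so it does not show that improvement lasts.

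The change costs SAP wording and no new data. The price is the small power loss shown above (.72 against .76 at rho 0.5) when the gain is complete at 3 months. The contrast needs responses linked within therapist, as the planned ANOVA already does. Values carried forward under LOCF would enter the contrast as they enter the ANOVA, and this change does not address that.
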